#### Adjunctive Compression Guidelines:

Upon successful deployment of the VASCADE VCS, adjunctive compression at the site may be used until arterial hemostasis is achieved (i.e., no pulsatile bleeding or a forming hematoma). TTH will not be recorded until adjunctive compression is no longer applied and arterial hemostasis is achieved. These times will be recorded on the Procedure Source Data Worksheet provided by the Sponsor (required).

**NOTE: Manual compression devices should not be used for achieving initial arterial hemostasis to ensure accurate recording of TTH.**

#### Light Compression Guidelines:

If the subject experiences slight oozing from cutaneous or subcutaneous tissues, characterized by the absence of pulsatile arterial flow, light compression methods (i.e., sand bags, compression bandages/devices, and light manual pressure) may be used to manage oozing. Any light manual pressure applied to control oozing should be documented on the Source Document Worksheet.

#### 7.4.4. Post-Operative

After hemostasis is achieved, the access site should be closely monitored at least every 15 minutes for the first hour, and then according to standard of care to confirm hemostasis.

##### Ambulation

Subjects should be ambulated according to institution's standard practice. Any incidents of delay in ambulation (> 1 hour beyond stated standard of care for each site) should be documented on the Ambulation eCRF and a Protocol Deviation eCRF should be completed for non-medical delays > 1 hour. Record the following information on the Post-Procedure Source Data Worksheet provided by the Sponsor (required):

- **T7** TTA: time that subject was able to stand and ambulate at least 20 feet without evidence of arterial re-bleeding at the access site.

##### Hospital Discharge

Prior to hospital discharge, all subjects will be evaluated for symptoms of lower extremity neuropathy in the ipsilateral limb that were not existing prior to the index procedure (i.e., paresthesias, numbness, weakness), including an assessment of severity. Record the following information on the Post-Procedure Source Data Worksheet provided by the Sponsor (required):

- **T8** TTD: time of discharge from the facility.

Subjects should be discharged according to institution's standard practice. Any incidents of access site arterial re-bleeding, or delay in time to discharge should be documented on the Discharge eCRF.

#### 7.5. Follow-up

All enrolled subjects are required to complete an office visit between days 1-15, and a 30 (+/- 7) day telephone follow-up. Depending on each institution's

standard practice for follow-up visits, subjects may return to the office for access site assessment any time between 1 and 15 days post-procedure. The subject should be instructed that a follow-up telephone assessment will be conducted between day 23 and 37 to complete the study. It is important that all subjects are contacted within the 30 (+/- 7) day window to determine Procedural Success.

During both the office visit and telephone follow-up, the subject should be queried regarding any complications they experienced after hospital discharge and the status of the access site wound should be assessed. All subjects will be evaluated for symptoms of lower extremity neuropathy in the ipsilateral limb that were not existing prior to the index procedure (i.e., paresthesias, numbness, weakness), including an assessment of severity.

In the event of refusal to return to the clinic, a protocol deviation will be reported and a telephone follow-up will be completed.

## **7.6. Study Exit**

Once the subject has completed the follow-up visit or has withdrawn, they should be exited from the registry provided they do not have any conditions that require continued follow-up. The date of exit and subject status will be recorded.

## **8. Assessment of Procedural Outcomes**

### **8.1. Primary Procedural Outcomes - Performance**

Time to hemostasis (TTH) is defined as the elapsed time between Cardiva VASCADE™ VCS removal and first observed and confirmed arterial hemostasis. The time to hemostasis will be measured in hour (hh):minutes (mm):seconds (ss). (TTH = T6 – T5).

### **8.2. Secondary Procedural Outcomes - Performance**

Time to ambulation (TTA) is defined as elapsed time between device removal and when subject first stands and walks 20 feet without evidence of arterial re-bleeding from the access site. The time to ambulation will be measured in hour (hh):minutes (mm). (TTA = T7 – T5).

Time to discharge (TTD) is defined as elapsed time between device removal and when subject is actually discharged from the facility. The time to ambulation will be measured in hour (hh):minutes (mm). (TTA = T8 – T5).

Device Success is defined as the ability to deploy the delivery system, deliver the collagen, and achieve hemostasis with the Cardiva VASCADE™ VCS alone or with adjunctive compression.

Procedure Success is defined as attainment of Device Success and freedom from major access site closure-related complications through 30 days.

### **8.3. Primary Procedural Outcomes - Complications**

The primary procedural complication composite to be evaluated is the 30-day patient incidence rate of combined major access site closure-related complications. Major complications include:

- Access site closure-related bleeding requiring transfusion;
- Vascular injury requiring repair (via surgery, ultrasound guided compression, transcatheter embolization or stent graft);
- New ipsilateral lower extremity ischemia causing a threat to the viability of the limb and requiring surgical or additional percutaneous intervention;
- Access site-related infection requiring intravenous antibiotics and/or extended hospitalization;
- New onset neuropathy in the ipsilateral lower extremity requiring surgical repair;
- New onset permanent nerve injury in the ipsilateral lower extremity. (> 30 days).

### **8.4. Secondary Procedural Outcomes - Complications**

The secondary procedural complication composite to be evaluated is the 30-day patient incidence rate of combined minor access site closure-related complications. Minor complications include:

- Access site-related bleeding requiring greater than 30 minutes to achieve initial arterial hemostasis;
- Access site-related hematoma > 6 cm documented by ultrasound;
- Late access site-related arterial bleeding requiring intervention (following hospital discharge);
- Ipsilateral lower extremity arterial emboli documented by ultrasound/imaging;
- Ipsilateral deep vein thrombosis documented by ultrasound;
- Access site-related vessel laceration;
- Access site wound dehiscence;
- Localized access site infection treated with intramuscular or oral antibiotics;
- Arteriovenous fistula not requiring treatment, documented by ultrasound/imaging;
- Pseudoaneurysm requiring thrombin injection or fibrin adhesive injection;
- New onset access site-related neuropathy in the ipsilateral lower extremity not requiring surgical repair.

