## 6. Written Informed Consent – 21 CFR 50 Protection of Human Subjects

Patients who meet general entry criteria will be asked to sign the registry-specific, Institutional Review Board (IRB) -approved Informed Consent form before any registry-specific data are collected. The informed consent will be reviewed and approved by Cardiva Medical prior to IRB submission to ensure compliance with all applicable requirements of 21 CFR 50.

Since this is a post-market registry, subjects will be treated and followed according to the institution's accepted standard of care and in adherence with the protocol.

There are no additional tests. Standard of care for office visit follow-up timing for these subjects varies between sites and procedure-types, therefore a wide window for the office visit has been established to accommodate as many subjects as possible. The required office visit may be performed between 1-15 days post-procedure, followed by a telephone follow-up between 23-37 days for final assessment of any complications. These contacts are required so that Procedure Success can be evaluated at 30 days, and to ensure that outcomes are consistently reported according to industry standards.

Study personnel should explain that even if a patient agrees to participate in the registry and signs an informed consent form, the Investigator may still determine that the patient is not a suitable candidate for the registry.

A Screening/Enrollment Log will be maintained to document select information about candidates who are consented, but who are not enrolled due to failure to meet the entry criteria.

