**Table 1. Registry Event Schedule**

	Up to 8 Weeks Before Procedure	Procedure	Post-Procedure/ Hospital Discharge	1-15 Days Post-Procedure	23-37 Days Post-Procedure
Informed Consent 	X				
Demographics/ Medical History / Risk Factors	X				
Index limb assessment 	X		X	X	X
Femoral access site assessment (angiographic)		X	X	X	X
Anticoagulant/antiplatelet regimen 	X	X	X		
Pre-op Inclusion / Exclusion Criteria assessment	X				
Laboratory tests 	X				
Intra-procedural Exclusion Criteria assessment & acknowledgement of intent to enroll		X			
Treated with VASCADE VCS		X			
TTH determination		X			
TTA determination			X		
TTD determination			X		
Procedure Success		X			X
Adverse Events 		X	X	X	X
Office Visit				X	
Telephone follow-up					X

 If informed consent is obtained > 30 days prior to procedure, the subject's verbal re-confirmation of consent should be documented in the medical record prior to the procedure.

 Index limb assessment includes Rutherford Classification, assessment of peripheral pulses, any wounds, amputation history and/or planned amputation, existing neuropathy, and ambulatory status.

 Specific medication regimen within 24 hours prior to enrollment through completion of index procedure.

 For subjects on warfarin, INR should be taken within 24 hours before procedure. "Laboratory tests" refer to exclusion criteria requirements, according to standard of care for these procedures at each site.

 Required adverse event reports: serious, device-related injury or death; minor or major access site closure-related complications; any event that is deemed by Investigator to be clinically significant AND related to the device, the access site or the index limb (See Section 13).

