## **18.2 Definitions**

### **ACCESS SITE-RELATED HEMATOMA > 6 CM**

A localized collection of extravasated blood in subcutaneous tissue at the access site measuring > 6 cm at its widest point, documented on ultrasound.

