**HEMATOMA**

A localized collection of extravasated blood in subcutaneous tissue, usually clotted. A metric ruler should be used to measure the widest portion of the hematoma.

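### Hematoma > 6 cm counts as a minor complication only with ultrasound documentation, but no ultrasound is scheduled or triggered after closure and the instructed ruler reading does not qualify

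*Combined protocol and SAP*

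**What the plan says.** Section 8.4 includes in the minor composite "Access site-related hematoma > 6 cm documented by ultrasound". The Synopsis has the same condition, and the matching entry in Section 18.2 requires a collection "measuring > 6 cm at its widest point, documented on ultrasound". The ultrasound requirement is thus stated consistently in three places.

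Section 18.2 also has a general entry for hematoma, which gives a bedside method: "A metric ruler should be used to measure the widest portion of the hematoma". Nothing says that this reading satisfies the > 6 cm component.

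On what is done after closure:

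- Section 6 says of the registry as a whole: "There are no additional tests".
- Section 7.4.4 asks for site checks every 15 minutes for the first hour, "and then according to standard of care to confirm hemostasis".
- The Hospital Discharge part of 7.4.4 asks for a neuropathy evaluation and adds: "Any incidents of access site arterial re-bleeding, or delay in time to discharge should be documented on the Discharge eCRF".
- Section 7.5 has subjects return for an access site assessment, asks about complications since discharge, and says "the status of the access site wound should be assessed". It asks for no size.
- Table 1 has no ultrasound row. Its femoral access site row is marked at discharge and at both follow-up contacts, but is labelled angiographic.

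Section 9.2.3.2 reports the minor composite as a proportion with a 95% Wilson interval, and each component separately. Section 9.2.1 adds subgroup presentations.

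**The concern.** A component that counts only when a particular test has been done needs that test to be applied in the same way to everyone. Here the test is left to local practice at up to seven sites. The same visible hematoma of more than 6 cm enters the minor composite at a site that scans and stays out at a site that does not, unless the subject qualifies through another component. The error runs one way, toward a lower minor rate. If scanning habits differ between, say, inpatient and outpatient facilities (an assumption), that subgroup presentation would partly show scanning rather than complications.

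Deep vein thrombosis, arterial emboli and arteriovenous fistula also carry imaging conditions. Hematoma differs because the protocol itself specifies a bedside measurement and then gives it no role in the endpoint. Section 1.1 criticises published studies for inconsistent methods and definitions and sets consistent prospective collection as the aim, so a site-dependent component works against the registry's own purpose.

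**Working it through.** The plan has no figure to reproduce: Section 9.3 judges 100 subjects sufficient without a calculation. The check has two parts.

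**1. Can a large hematoma fail to count under the plan as written?**

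- Counted definition (8.4, 18.2): > 6 cm and ultrasound documentation.
- Instructed measurement (18.2, general entry): ruler, widest portion.
- Scheduled or triggered ultrasound (6, 7.4.4, 7.5, Table 1): none.

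A hematoma measured by ruler at more than 6 cm and not scanned does not meet the component. A scan under standard of care is allowed, so the component can be met, but only at the site's discretion.

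**2. How many could be missed?**

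Inputs, from the RESPECT tables in Attachment 2 (VASCADE arm, hematoma > 6 cm):

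| Stratum | Events / n | Rate | Wilson 95% interval |
|---|---|---|---|
| Interventional | 0/139 | 0% | 0 to 2.69% |
| Diagnostic | 1/136 | 0.74% | 0.13 to 4.05% |
| Pooled | 1/275 | 0.36% | 0.06 to 2.03% |

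With zero events the Wilson upper limit is z²/(n + z²) = 3.84/(139 + 3.84) = 2.69%.

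Let h be the true rate of hematoma > 6 cm and s the share that are scanned (assumed). Then

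missed hematomas per 100 subjects = 100 × h × (1 − s).

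| h | s = 0 | s = 0.5 | s = 1 |
|---|---|---|---|
| 0 (interventional estimate) | 0 | 0 | 0 |
| 0.36% (pooled) | 0.36 | 0.18 | 0 |
| 2.69% (interventional upper limit) | 2.69 | 1.34 | 0 |

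These are missed hematomas, not subjects lost from the composite. If a share o of the missed cases have another minor component, the composite loses 100 × h × (1 − s) × (1 − o). The documents do not give o. Since 1 − o cannot exceed 1, the table is an upper bound for the composite at each h and s.

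For scale, the minor rate in RESPECT interventional VASCADE patients was 1/139 = 0.72% (Wilson 0.13 to 3.96%), from bleeding over 30 minutes alone. In the registry, 0 events in 100 would be shown as 0% with an upper limit of 3.84/(100 + 3.84) = 3.70%.

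**The case against.** The strongest defence is that imaging confirmation is a deliberate choice for specificity, applied also to thrombosis, emboli and fistula, in a standard-of-care registry that adds no tests. The general hematoma entry and the counted component can serve different purposes without contradiction. This stands as a reason to keep the ultrasound-documented count as the main result. It does not remove the dependence on scanning habit.

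A reader might also infer that an unscanned hematoma disappears from the registry, or survives only if the investigator calls it clinically significant. The documents do not support that:

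- Section 13.3 separately requires serious, device-related events to be reported, without a clinical-significance judgement.
- Under 7.4.3, an immediate hematoma that raises suspicion of a back-wall or second puncture leads to device removal and manual compression. Section 9.2.2.1 reports conversions.
- A forming hematoma means that hemostasis has not been achieved (7.4.3), so it lengthens time to hemostasis.
- Access-site-related delays appear in the ambulation and discharge summaries (9.2.1).
- The subject may still enter the minor composite through compression beyond 30 minutes or late re-bleeding needing intervention.

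What remains is narrower: these routes do not restore the hematoma component, and they restore the composite only for subjects who meet another component.

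It is also fair that the eCRFs and worksheets are not in the documents, so diameter and imaging may already be captured. Independent adjudication covers minor complications, but nothing says that the adjudicator may waive the ultrasound condition.

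**Conclusion.** The point holds in limited form. Under the current definition, the hematoma > 6 cm component, and the minor composite for subjects with no other minor component, depend partly on discretionary scanning. The likely direction is an undercount. Its size cannot be derived from the documents and may be zero. With nothing scanned, it is at most 0, 0.4 or 2.7 hematomas per 100 subjects at the three RESPECT-based rates. With half scanned (assumed), it is 0, 0.2 or 1.3.

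These figures rest on RESPECT rates standing in for the true rate. RESPECT excluded clinically significant peripheral vascular disease, and its hematoma definition is not given. If it also needed imaging, its own rates could be low. The 2.7 figure combines a confidence limit with no scanning at any site and should not be read as an expected loss.

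Two further inferences should be resisted. The RESPECT tables list the item without an ultrasound condition, but a row label is not a definition, so no inconsistency with RESPECT is shown. Nor are the headline results at risk: time to hemostasis, the major composite, Device Success and Procedure Success do not depend on this definition. The outcome is secondary and descriptive, with no test or threshold. This is worth improving, at low priority.

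**What to change.** At discharge and at the office visit, record the widest ruler-measured diameter of any hematoma and whether an ultrasound was done, if the eCRF does not already hold these. Report the hematoma > 6 cm component and the minor composite two ways:

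- ultrasound-documented, as now defined, kept as the main result;
- ruler or ultrasound, as a supporting result.

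The telephone contact cannot supply a ruler reading, so ruler readings for the second count come from discharge and the office visit only. State this in the table footnote.

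The cost is at most two eCRF fields and two extra table lines, with no added test. The downside is that a ruler-based count is less specific than imaging and may make the minor rate slightly less favourable. Showing both counts, with the number of hematomas scanned, lets the reader see how far the result depends on scanning.

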## **9. Statistical Considerations**

### **9.1. Analysis Populations and Data Handling Conventions**

#### **9.1.1. Intent to Treat (ITT) Population**

All subjects who receive any portion of the Cardiva VASCADE™ VCS device treatment under this protocol (i.e., intention to enroll acknowledged by Investigator prior to introduction of the device; subject is then enrolled at time of device introduction) will be included in the primary, ITT performance and complication analyses.

Subjects who do not receive any portion of the VASCADE™ VCS but instead receive manual compression, a VASCADE VCS commercial device (i.e., outside of the registry), or another approved closure device instead (i.e., by error or by Investigator choice), will not be enrolled and are therefore excluded from all analyses.

#### **9.1.2. Per Protocol (PP) Population**

As secondary analyses, all subjects who have the collagen deployed and meet all I/E criteria will be included in the PP performance and complication analyses.

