## 5.2. Withdrawal of Subjects

While withdrawal is discouraged, subjects may withdraw from the registry at any time, with or without reason and without prejudice to further treatment. In all cases of withdrawal, the reason(s) for withdrawal (if given) will be recorded upon registry termination.

In addition, the Investigator may withdraw the subject due to any reason determined by the Investigator to be in the best interest of the subject.

Subjects withdrawn from the registry prior to hemostasis (e.g., after enrollment and prior to deployment of the collagen plug) should be converted to conventional means (manual compression) to achieve hemostasis.

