### 9.2.2.3 Secondary Performance Outcomes Analyses

Secondary performance outcomes to be reported include time to ambulation (TTA), time to discharge (TTD), and proportions of device success and procedure success as defined in Section 8.2 in both the ITT and PP cohorts. The analyses will be as described in Section 9.2.1.

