## WARNINGS

- Do not reuse or re-sterilize. The VASCADE VCS is intended to be used once only for a single patient. Product reuse or re-sterilization, may result in transmission of infectious or blood borne diseases and/or death.
  - Do not use if components or packaging appear to be damaged or defective or if any portion of the packaging has been previously opened. Damaged or opened packages may compromise product functionality.
  - Do not use if product is beyond the expiration date. Product performance has not been established beyond the labeled shelf life.
  - Do not deploy the VASCADE Disc in a stent. Do not pull the deployed VASCADE disc through a stent. Damage to the product may occur.
  - Do not use VASCADE if access is through a previously placed permanent closure device such as a metal clip. Interference between the two closure devices may result.
  - Do not deploy the Collagen Patch if there is a suspicion that the VASCADE Vascular Closure Disc is not seated against the intimal aspect of the arteriotomy site. Partial or complete obstruction of blood flow may result.
  - Do not deploy a second collagen patch at the same access site within 90 days. Safety has not been established.
- 

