- Apply gentle tension on the Black Actuator until temporary hemostasis is achieved. Note whether any portion of the White Marker Stripe, which is located near the distal aspect of the Black Sleeve, is visible above the skin. If it is, then the length of the tissue tract is less than 2.5 cm, indicating the tissue tract may not be long enough for the Collagen Patch.

**WARNING:** If any portion of the White Marker Stripe is showing DO NOT RELEASE the Collagen Patch as this may increase the risk of infection.

**NOTE:** If any portion of the White Marker Stripe is showing and the collagen patch is not to be deployed continue the procedure as follows:

**For diagnostic cases:** the VASCADE VCS Catheter should be removed by collapsing the Disc and then manual compression can be applied per institutional protocol.

**For anti-coagulated patients:** the Clip may be applied to the VASCADE VCS Catheter on the skin surface as shown in **Figure 10** to maintain temporary hemostasis. The device may then stay in dwelling to allow time for the ACT level to normalize. The device can then be removed followed by application of manual compression per institutional protocol to achieve final hemostasis.

11. Once temporary hemostasis is achieved, apply the Clip to the Black Sleeve at skin level as shown in **Figure 10**. Utilize fluoroscopy to verify that the deployed Disc is positioned against the intimal surface of the arteriotomy by noting the position of the more proximal radiopaque marker. The marker should be at the arteriotomy site which can be verified by comparing its location with the location of the arteriotomy documented at the time of the introducer sheath insertion. The Collagen Patch is immediately proximal to this Marker Band. The Distal Marker Band locates the distal end of the Disc.

**CAUTION:** Applying too much upward tension on the Black Actuator may cause disc to pull out of vessel. Should this occur, convert to your **institution's manual compression protocol**.

**WARNING:** It is important to ensure that the Disc is in contact with the intimal aspect of the arteriotomy before deploying the extra-vascular Collagen Patch to avoid releasing the Collagen Patch in the vessel. This step requires fluoroscopy (**Figure 11**).

Fig. 10 – Apply Clip to Black Sleeve at skin level

[figure not shown]

Fig. 11 – Fluoroscopic image demonstrating proper position of Disc against the arteriotomy

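### The per-protocol set requires collagen deployment, which is itself part of Device Success and Procedure Success, so the PP versions of those two rates are conditioned on their own outcome

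*Combined protocol and SAP*

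**What the plan says.** Section 9.1.2 defines the PP population for secondary analyses: "all subjects who have the collagen deployed and meet all I/E criteria will be included in the PP performance and complication analyses".

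Section 8.2 defines the two outcomes. "Device Success is defined as the ability to deploy the delivery system, deliver the collagen, and achieve hemostasis", with the device alone or helped by adjunctive compression. "Procedure Success is defined as attainment of Device Success and freedom from major access site closure-related complications through 30 days".

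Section 9.2.2.3 lists among the secondary analyses the "proportions of device success and procedure success as defined in Section 8.2 in both the ITT and PP cohorts".

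By contrast, the ITT population in Section 9.1.1 takes in everyone who receives any part of the device treatment, and it is the primary set. Section 7.2 places enrollment at the moment the device enters the body. The Instructions for Use (IFU, Attachment 2) expose the collagen only later, at step 12. A subject can therefore be enrolled and never have collagen deployed.

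**The concern.** Failure to deliver the collagen is one of the things Device Success exists to count. If such subjects leave the denominator, the PP rate still carries the Section 8.2 name but answers a different question: how often the device achieved hemostasis once the collagen was in place. That is a legitimate descriptive quantity, but it is not the outcome defined in Section 8.2. Procedure Success inherits the problem.

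The documents foresee subjects of this kind:

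- The IFU caution at step 11 warns that "Applying too much upward tension on the Black Actuator may cause disc to pull out of vessel", with conversion to manual compression. This comes before the step that exposes the patch.
- The IFU Warnings say "Do not deploy the Collagen Patch if there is a suspicion that the VASCADE Vascular Closure Disc is not seated against the intimal aspect".
- Section 5.2 provides for withdrawal "after enrollment and prior to deployment of the collagen plug".

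The first two routes match no inclusion or exclusion criterion in Section 5.1, so only the collagen condition takes those subjects out of PP.

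At stake is how a PP Device Success or Procedure Success figure will be read once it is quoted without its denominator rule. PP time to hemostasis and PP complication rates are not part of this point.

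**Working it through.** **Direction.** Let S be success (Device or Procedure) and C be collagen deployed. Section 8.2 makes delivery a requirement of S, so every success lies in C. Then

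P(S | C) = P(S and C) / P(C) = P(S) / P(C) ≥ P(S),

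with equality only if every subject has collagen deployed or there are no successes. As a check, all count combinations up to 30 subjects were enumerated, with missing outcomes dropped as Section 9.1.3 implies. In none of 319,176 configurations was the rate among collagen-deployed subjects below the ITT rate.

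**Inputs for scale.** The plan gives no expected success rate or non-deployment rate, so there is no figure of its own to reproduce. The IFU gives RESPECT Device Success in Table 6:

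- interventional: 135/139 = 97.1%
- diagnostic: 128/136 = 94.1%
- total: (128 + 135)/(136 + 139) = 263/275 = 95.6%, stated as 96%

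Rounded to 100 enrolled (the maximum in Section 4.2), this suggests 3 failures from the interventional rate or 4 from the total. The registry enrolls interventional procedures only, so 3 is the closer analogue. Both are assumptions, because RESPECT excluded patients with clinically significant peripheral vascular disease.

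**Formula.** With f failures in 100, k of them non-deployments, and the eligibility condition set aside, the PP rate is (100 − f)/(100 − k). Intervals are 95% Wilson, as Section 9.2.1 specifies.

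| k | f = 3 | f = 4 |
|---|---|---|
| 0 (same as ITT) | 97/100 = 97.0% (91.5–99.0) | 96/100 = 96.0% (90.2–98.4) |
| 1 | 97/99 = 98.0% (92.9–99.4) | 96/99 = 97.0% (91.5–99.0) |
| 2 | 97/98 = 99.0% (94.4–99.8) | 96/98 = 98.0% (92.9–99.4) |
| 3 | 97/97 = 100% (96.2–100) | 96/97 = 99.0% (94.4–99.8) |
| 4 | not applicable | 96/96 = 100% (96.2–100) |

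For Procedure Success, take f = 4 and assume one major complication among the 96 device successes. ITT is 95/100 = 95.0% (88.8–97.8). With k = 4, PP is 95/96 = 99.0% (94.3–99.8).

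**The eligibility condition.** This second PP requirement can move the rates either way. From 96/100, removing two ineligible successes gives 94/98 = 95.9%; removing two ineligible failures gives 96/98 = 98.0%. The full PP rate therefore need not exceed the ITT rate. The one-way effect belongs to the collagen condition alone. Section 14.3 grants no eligibility waivers, so the eligibility effect should be small.

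**Can a reader undo the conditioning?** Not fully. Suppose ITT is 96/100 and PP is 95/97. Failures fall from 4 to 2 and successes from 96 to 95, so 2 failures and 1 success left PP. The 2 failures could include 2, 1 or 0 non-deployments. The proportion converted to manual compression (Section 9.2.2.1) does not help, because it is not split into conversions before and after deployment.

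**Limits.**

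- A pre-deployment withdrawal is a failure only if it is scored as one. Left as missing under Section 9.1.3, it adds nothing to the PP rate.
- The IFU also says: "If any portion of the White Marker Stripe is showing and the collagen patch is not to be deployed continue the procedure as follows". Such a subject may leave PP through the 2.5 cm tissue-tract exclusion (Section 5.1.3, item 13) as well as through the collagen condition.
- A patch removed during sleeve retraction (IFU step 12 note) is ambiguous, because Section 9.1.2 does not define deployed. A broader reading shrinks the lift but cannot reverse it.

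**The case against.** The strongest reply is that this is ordinary per-protocol practice, openly stated. Section 9.1.2 puts the collagen condition in its one-sentence definition, ITT is primary and appears alongside, the registry is descriptive, and no decision turns on a PP success rate. PP Device Success would still count failures of hemostasis after deployment, and PP Procedure Success would still count major complications. The IFU cautions show that non-deployment is possible, not that it is frequent, and Section 12.2 says the investigators were chosen for experience. The two sets could give the same rates. On this view a footnote would be enough, and restricting the rates to ITT would also discard a success rate among eligible subjects.

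Much of this stands. The consequence is small, the size is unknown, and the top of each range needs every failure to be a non-deployment, which nothing in the documents supports. What does not stand is the appeal to convention. Restricting to treated subjects is usually harmless to an outcome's meaning, but here receiving the collagen is part of the outcome. Stating the condition in Section 9.1.2 does not tell the reader that the PP success rates are conditional on a piece of their own definition, and the planned tables do not let the reader recover the missing count. The lost eligibility-restricted rate matters little when no waivers are granted.

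**Conclusion.** The concern holds, as a minor point. Followed as written, the plan produces PP Device Success and Procedure Success rates from which non-deployment failures have been removed by construction. The direction is certain for the collagen condition taken alone: up or unchanged. The size cannot be known from the documents. Under assumed Device Success failure counts of 3 or 4 in 100, borrowed from RESPECT, the lift in Device Success is 0 to 3 or 0 to 4 percentage points. At the extreme of 4 non-deployments, PP shows 100% with a lower limit about 6 points above the ITT one (96.2% against 90.2%). A different antegrade failure rate would change these ranges. The ITT results are unaffected.

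**What to change.** Amend Section 9.2.2.3 so that Device Success and Procedure Success, as defined in Section 8.2, are reported in the ITT population only. If a rate in the collagen-deployed set is still wanted, give it a title that states the condition, such as hemostasis with the device given collagen deployed, and do not use the Section 8.2 names. Show beside it the number of enrolled subjects without collagen deployed, separately from those removed for eligibility reasons. State in Section 9.1.2 whether a patch removed during sleeve retraction counts as deployed for this analysis set.

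The IFU offers a precedent for this openness: Table 6 gives Device Success on all treated subjects, and its footnote gives the rates without 6 instances of not following the instructions, with that number stated.

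The cost is SAP wording and one extra count from data already collected. The downside is that the more favourable PP success figures are lost or renamed, and that a success rate restricted to eligible subjects is no longer shown.
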